## **Data Analysis**

Before data analysis is carried out, the data is checked for completeness and accuracy, tabulated, coded, and entered into the computer. The next data analysis aims to describe the dependent and independent variables so that it can help further analysis in more depth. Apart from that, descriptive analysis is also used to determine the characteristics of the research subjects, who are the research samples.

Data analysis to see an overview of the proportions of each variable that will be presented descriptively can be broken down into descriptive analysis and hypothesis testing. Numerical scale data such as age and others are presented with a mean and standard deviation, a maximum value, and a minimum value. The sample characteristic data in the form of categorical data is presented in a frequency distribution table. Data is recorded in the research form that has been created, then editing, verification, coding, and data entry are carried out, and then data analysis

is carried out. Statistical analysis according to research objectives and research hypotheses Data are presented as percentages (%) for categorical variables and mean  $\pm$  standard deviation (SD) for continuous variables. Statistical analysis begins with this normality test aims to find out whether the data is normally distributed or not. The statistical test used to test the data is normally distributed or not, with Shapiro Wilks (because n is less than 50). Numerical variables between pairs of two groups is compared using the paired T test if the data is normally distributed and the alternative Wilcoxon test. Numerical variables between pairs of more than two groups is compared using the repeated ANOVA test if the data is normally distributed and the alternative Fredman test. The McNemar and Marginal Homogeneity tests are used for paired categorical data. The significance of statistical test results is determined based on a p value of  $<0.05$ .

The data obtained was recorded in a special form and then processed using the SPSS version 24.0 for Windows program.

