### ***Research Question***

More specifically, the following research question needs to be addressed :

Can sEMG parameters predict upper extremity motor function recovery in acute stroke patients?

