### ***Study Objective***

The aim of the study are:

To know if sEMG parameters can predict upper extremity motor function recovery in acute stroke patients

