**Hypothesis :**

Based on the framework and premises above, the hypothesis is formulated as follows:

H0 : sEMG parameters cannot predicts upper extremity motor function recovery in stroke patients

H1: sEMG parameters can predicts upper extremity motor function recovery in stroke patients (premise 1,2,3,4,5)

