## Study Variable

Independent variables:

1. Type of stroke
2. Stroke severity
3. Recurrent stroke

Dependent variables:

1. MMT score
2. FMA-UE score
3. Electrical activity of deltoid muscle
4. Electrical activity of biceps muscle
5. Electrical activity of triceps muscle
6. Electrical activity of wrist flexors muscle
7. Electrical activity of wrist extensors muscle

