## Sample Size Determination

Samples are taken from research subjects that meet the inclusion criteria.

The sample size to test the pair averages then the large determination of the sample, carried out on the basis of statistical calculations by setting the 95% confidence level of the two-way hypothesis and the power test 95%.

Sample determination for categorical numerical analytical research pairs using the formula:

$$n_1 = n_2 = \left( \frac{(Z_\alpha + Z_\beta)S}{X_1 - X_2} \right)^2$$

Where:

$Z_\alpha$  = alpha standard deviation

$Z_\beta$  = beta standard deviation

$S$  = combined standard deviation.

$X_1 - X_2$  = average minimal difference that is considered significant

Type I error is determined as 5%, hence two-ways hypothesis  $Z\alpha = 1,96$

Type 2 error determined as 5%, hence  $Z\beta = 1,64$

Based on the formula, the value is entered into the sample size formula as follows:

$$n_1 = n_2 = \left( \frac{(Z_\alpha + Z_\beta)S}{X_1 - X_2} \right)^2$$

$$n_1 = n_2 = \left( \frac{(1,96 + 1,64) * 1}{1} \right)^2$$

$$= 12,96 \approx 13$$

The minimum sample size for the pre-post test group is 13 people. The minimum number of samples required is 13 samples. The minimum sample number is added to the 10% possibility of sample exclusion so that the minimum sample size is  $13 + 1.3 = 14.3 \approx 15$  samples.

According to Gay and Diehl (1992), the sample must be as large as possible. This opinion assumes that the more samples taken, the more representative they will be and the results can be generalized. The sample size depends on the type of research:

1. The research is descriptive, so the minimum sample = 10% of the population
2. Correlational research, minimum sample is 30 units
3. Comparative causal research, the sample is 30 units per group
4. Experimental research, the minimum sample is 15 units per group

Based on the opinion of Gay and Diehl (1992), the minimum sample for this study for comparative analysis is 30 people. Based on the formula above, the minimum sample size for this research is adequate, so the minimum sample size is 30 samples.

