## Dummy Table

Table 2. Dummy Table

Variable	In Hospital				Follow Up			Difference in change at 3 months
	3 days	Discharge	P-Value	1 Months	2 Months	3 Months	P-Value	
MMT score								
FMA-UE score								
Contraction								
Length of contraction								
Amplitude								

Note: For numerical data, the p value is tested using the paired T test if the data is normally distributed and the alternative Wilcoxon test if the data is not normally distributed. Then, to compare numerical variables between pairs of more than two groups using the repeated ANOVA test if the data is normally distributed and the alternative Fredman test. The significance value is based on a p value of <0.05. The \* sign indicates a p value <0.05, meaning it is significant or statistically significant.

Table 3. Characteristic Table

Variables	p-Value
Sex	
Women	
Men	
Age	
Length of stay	
Stroke diagnosis	
Ischemic stroke	
Haemorrhagic stroke	
Stroke side	
Right hemisphere	
Left hemisphere	
Dominant Hand	
Right	
Left	
Stroke severity	
Minor stroke	
Moderate stroke	
Moderate to severe stroke	
Severe stroke	
Stroke risk factor	
Hypertension	
Diabetes Mellitus	
Heart disease	
Dyslipidemia	
Smoking	
Recurrent stroke	
Yes	
No	

Note: categorical data is presented in number, frequency, and percentage, while numerical data is presented in mean, median, standard deviation, and range.

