## Outcome Measures

The investigator assessed the outcome measures. The outcome measures are MMT score, FMA UE score, sEMG parameters (contractions, length of contraction, and amplitude). It is measured at 3 days of stroke onset, the day of discharge from hospital, 1 months, 2 months and 3 months after stroke onset.

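### No planned test addresses the hypothesis: every named hypothesis test is a paired comparison, and none relates a patient's early sEMG to that patient's later FMA-UE

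*Combined protocol and SAP*

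**What the plan says.** Three places set the aim, and all concern prediction:

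- Research Question: "Can sEMG parameters predict upper extremity motor function recovery in acute stroke patients".
- Study Objective: "To know if sEMG parameters can predict upper extremity motor function recovery in acute stroke patients".
- H1: "sEMG parameters can predicts upper extremity motor function recovery in stroke patients".

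The analysis sections describe something else.

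- **Data Analysis.** For two time points, "Numerical variables between pairs of two groups is compared using the paired T test", with Wilcoxon as the alternative. For more than two, repeated-measures ANOVA or Friedman. For paired categorical data, McNemar and marginal homogeneity. Shapiro-Wilk is also named, but only as a normality check.
- **Dummy Table, Table 2.** There is one row per variable (MMT, FMA-UE and three sEMG parameters), with visits as columns. One p-value sits with 3 days and discharge, and another with months 1, 2 and 3. The note repeats the paired test and adds the method "to compare numerical variables between pairs of more than two groups using the repeated ANOVA test".
- **Study Variable.** The independent variables are stroke type, severity and recurrence. sEMG is among the dependent variables, beginning with "Electrical activity of deltoid muscle", in the same list as FMA-UE.
- **Outcome Measures.** "The outcome measures are MMT score, FMA UE score, sEMG parameters (contractions, length of contraction, and amplitude").
- **Sample Size Determination.** The calculation is introduced as "The sample size to test the pair averages".
- **Operational Definition, Table 4.** Recovery is described as improvement but recorded as three FMA-UE severity bands (≤25, 26–45, 46–66). The FMA-UE row shows the same bands and is labelled numerical.

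**The concern.** A claim that sEMG predicts recovery concerns association across patients: do those with more early muscle activity end with better FMA-UE than those with less? A paired test on one variable asks whether its mean moved between visits. The two can come apart in either direction. FMA-UE may rise in nearly everyone while early sEMG says nothing about who rises most, or the mean may hardly move while early sEMG ranks patients well.

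The risk is practical. The literature review expects the largest improvement in the first weeks after stroke, so significant change over time is likely whatever sEMG contributes. Reading that significance as support for H1 would be a false conclusion on the study's only hypothesis.

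**Working it through.** **1. The plan's own figure.** Sample Size Determination uses Zα = 1.96, Zβ = 1.64, S = 1 and X1 − X2 = 1:

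n = ((1.96 + 1.64) × 1 / 1)² = 12.96, rounded up to 13. Adding 10%: 13 + 1.3 = 14.3, rounded up to 15.

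This reproduces exactly, but it is the formula for a within-patient mean change of 1 SD. The final 30 comes from a published rule of thumb for comparative analysis. No correlation or regression effect is given anywhere.

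**2. What the paired statistic contains.** With D = later value − earlier value, t = mean(D) / (SD(D)/√n). In the FMA-UE row no sEMG value enters, and in the sEMG rows no FMA-UE value enters. The repeated ANOVA is likewise run within one variable.

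**3. At the plan's own effect size.** Simulation with n = 30, 5,000 runs, and a 1 SD mean change in both sEMG and FMA-UE. The assumed correlation is between early sEMG and 3-month FMA-UE, unadjusted.

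| Test | Correlation 0 | Correlation 0.6 |
|---|---|---|
| Paired t, sEMG | 99.9% | 99.98% |
| Paired t, FMA-UE | 100% | 99.98% |
| Correlation test | 4.5% | 95% |

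**4. At smaller changes.** n = 30, 20,000 runs. Assumptions: Day-3 sEMG and Day-3 FMA-UE correlate 0.5; FMA-UE change has SD 1 and mean d; the partial correlation of change with Day-3 sEMG, given Day-3 FMA-UE, is ρ. Entries are rejection rates.

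| Test | ρ = 0 | ρ = +0.6 | ρ = −0.6 |
|---|---|---|---|
| Paired t, d = 0 | 4.9% | 4.8% | 4.9% |
| Paired t, d = 0.2 | 18.6% | 18.7% | 19.0% |
| Paired t, d = 0.3 | 35.8% | 35.0% | 35.4% |
| Paired t, d = 0.5 | 75.6% | 75.0% | 75.4% |
| Regression adjusted for Day-3 FMA-UE | 5% | 95% | 95% |
| Unadjusted correlation | 49–50% | 99.7% | 5% |

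Exact noncentral-t power for the paired test is 18.5%, 35.5% and 75.4% at d = 0.2, 0.3 and 0.5.

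**5. Repeated ANOVA over months 1, 2 and 3.** n = 30, within-visit error SD 0.707. Here 0/+0.6/−0.6 is the correlation of Day-3 sEMG with the patient's overall FMA-UE level, not a partial correlation. With visit means 0, 0.25 and 0.5 it rejects in 66.0/66.8/66.1%; with equal means, in 5.0/5.4/4.7%.

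**6. Power of the analysis H1 needs.** Fisher z with one covariate, two-sided 0.05: power = Φ(atanh(r)·√(n − 4) − 1.96). For r = 0.3 and n = 30: 0.3095 × √26 − 1.96 = −0.38, giving 35%. The number needed for 80% power is n = ((1.96 + 0.84)/atanh(r))² + 4. The values of r are assumptions.

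| Partial r | Power, n = 30 | Power, n = 27 | N for 80% |
|---|---|---|---|
| 0.3 | 35% | 32% | 86 |
| 0.4 | 58% | 53% | 48 |
| 0.5 | 80% | 75% | 31 |
| 0.6 | 94% | 91% | 21 |

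The 27 is 30 less the plan's 10% allowance.

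**The case against.** The strongest reply is that the plan leaves room. Data Analysis says in general terms that analysis follows the objectives and hypotheses. Table 2 has a column for difference in change at 3 months, Table 3 has a p-value column, and the conceptual framework and research flow figures are not visible. None of this fills the gap. The general phrase names no method, predictor, outcome or visit. The Table 2 column stays within one variable's row. Table 3 lists patient and stroke characteristics, with neither sEMG nor FMA-UE. What the figures show is unknown, but the named tests are legible and Table 2 agrees with them. McNemar and marginal homogeneity do not appear in Table 2, but they too are paired tests.

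A fair technical point is that the second simulation equates prediction with prediction beyond baseline. At ρ = 0 in that set-up, Day-3 sEMG still correlates 0.5/√2 = 0.35 with 3-month FMA-UE. H1 does not say which meaning is intended. This stands as a reason to label the two analyses separately. It does not rescue the paired tests, which ignore both meanings, as the first simulation shows with the unadjusted correlation.

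The simulations illustrate an algebraic fact and are not evidence about this cohort. The background calls earlier correlations modest or moderate, but those came from patients with no movement on MMT or who were initially flaccid, so they guide the choice of r only weakly. The proposed model is one reasonable option, and it leaves out the confounders listed under Study participants.

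**Conclusion.** The concern holds and must be fixed. The plan states a hypothesis about prediction and names no test that bears on it. This follows from the structure of the tests and needs no assumption about effect size. The simulated rates do rest on assumptions (n = 30, the stated correlations and mean changes), but the pattern is the same throughout: rejection by the planned tests tracks mean change and is unaffected by whether sEMG predicts recovery. The stated 95% power belongs to a paired 1 SD change and says nothing about H1.

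The definition of recovery in Table 4 is a smaller, related matter. It needs settling before the outcome for H1 can be fixed.

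**What to change.** **Data Analysis.** Make the primary analysis a linear regression of the numeric 3-month FMA-UE score (0–66) on one Day-3 sEMG parameter in one muscle, adjusted for Day-3 FMA-UE. Name the parameter and muscle before follow-up data are analysed. Test H1 on that coefficient; report it with its 95% CI and the gain in R² over Day-3 FMA-UE alone. State that the adjustment is a design choice, making H1 mean prediction beyond the baseline clinical score, and report the unadjusted correlation alongside. Because the score is bounded, check residuals and give a partial Spearman correlation as a sensitivity analysis. Five muscles × three parameters give 15 candidates; treat the other 14 as secondary or exploratory with Holm adjustment.

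**Other sections.** In Study Variable, list Day-3 sEMG as independent and 3-month FMA-UE as dependent. Add a row or table for this analysis to the Dummy Table, and keep the paired and repeated-measures tests as descriptions of change. In Operational Definition, give one definition of recovery. In Sample Size Determination, say that the 95% power does not apply to the primary analysis.

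**Cost.** This is wording only: no visit or measurement is added, since Day-3 and 3-month assessments are already scheduled, and SPSS 24 fits the model. The price is disclosed low power, and at the first Holm step power for a secondary candidate is only about 9% at r = 0.3 and 73% at r = 0.6 with n = 30. Complete pairs may also fall below 30: the entry criteria set no Day-3 window, although the first assessment is scheduled then, and patients may withdraw or miss follow-ups. If the sample stays at 30, present the result as an estimate with its CI. There is little room for the listed confounders as further covariates.

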### **Study participants**

Potential participants will be recruited by the main researcher

Inclusion criteria:

1. Patients who are hospitalized with upper extremity weakness due to stroke on the same side which confirmed with computed tomography (CT) scan or structural magnetic resonance imaging (MRI), in the acute phase
2. Men and women aged more than 18 years old
3. Willing to participate

Exclusion criteria:

1. Cognitive impairment (MoCA-Ina score less than 26)
2. Impaired consciousness (GCS score less than 15)
3. Unstable medical conditions at time of hospitalization
4. Patients with pacemaker

5. Having other injury or dysfunction in the impaired side of upper extremity that caused restrictions on the range of joint movement and muscle weakness, such as fractures, periarthritis, or moderate-severe pain
6. Diagnosis of other neurological disease or disorders in addition to stroke (e.g., traumatic brain injury, neuropathy or radiculopathy)
7. Get treated in isolation room
8. Hypersensitivity to gel electrodes

Drop out criteria:

1. Unable to do 2 or more follow up session
2. Withdrawn by themselves

Confounding factor:

1. Stroke location
2. Stroke size
3. Spasticity
4. Rehabilitation program
5. Compliance rehabilitation
6. Stroke risk factor

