## Research Work Procedure

This research collaborates with the ITB engineering team and the procedure of research is carried out as follows:

1. Selection of subjects according to the criteria of inclusion and exclusion.
2. Research subjects are given an explanation of the research procedure as well as signing informed consent to participate the research.
3. Research subjects who agree to participate in the study sign the informed consent
4. Data registration of the examination form in the medical record
5. Examination of vital signs to see contraindications for further examination. The subjects used a pulse oximetry during the subsequent examination.
6. Upper extremity function assessment is carried out using MMT and FMA UE.
7. Electrical activity recording of deltoid, biceps, triceps, wrist flexors and wrist extensors muscles is performed using sEMG is carried out as follows:
  - a. The subjects are positioned sitting at 60-90 degrees during recording. Put an arm pillow below the impaired hand.
  - b. Preparation of the sEMG (Biograph Infinity) machine for observation the contraction of muscles.
  - c. Clean the skin first using alcohol swab to reduce skin impedance

- d. Ground electrodes are attached to the bone structures in the elbow in the impaired side (olecranon)
- e. Electrodes with diameter 50 mm are placed in impaired side at the anterior deltoid, long head of the biceps, lateral head of the triceps according to the Surface Electromyography for the Noninvasive Assessment of Muscles (SENIAM) guidelines standard placement procedures (Figure 5). Bony anatomical landmarks of the medial and lateral humeral epicondyles were used for standard placement of the subsequent electrodes the wrist flexor and extensor muscle groups, as SENIAM does not offer placement guidelines for these muscles

Figure 5. Electrodes/sensor placement

- f. Each muscle is examined by positioning two electrodes on it, separated by a distance of one or two centimeters
- g. The electrodes are fixed when the electrical activity is clearly visible on the monitor with minimal noise

- h. Muscle signal data were collected for 30 minutes
  - i. During 30 minutes, the subjects do the protocol activity (Figure 6) as describe, for subjects with MMT 0, the researcher then performed a passive range of motion:
    - 00:01:00 (shoulder flexion)
    - 00:02:00 (rest)
    - 00:03:00 (shoulder flexion)
    - 00:04:00 (rest)
    - 00:05:00 (shoulder flexion)
    - 00:06:00 (rest)

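### The month 1, 2 and 3 comparison, as normally run, leaves out any patient who misses one follow-up, although the drop-out rule keeps that patient; the loss is probably small and depends on attendance

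*Combined protocol and SAP*

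**What the plan says.** Outcomes are measured at 3 days, at discharge, and at "1 months, 2 months and 3 months after stroke onset" (Outcome Measures). The examination form labels exactly the last three as follow-ups.

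Under Data Analysis, numerical variables at more than two paired time points are "compared using the repeated ANOVA test if the data is normally distributed and the alternative Fredman test". The note to Table 2 (Dummy Table) repeats this: "to compare numerical variables between pairs of more than two groups using the repeated ANOVA test if the data is normally distributed". Table 2 has a column for each of months 1, 2 and 3 and one p-value after them. It also has a separate p-value for 3 days against discharge, and a last column headed "Difference in change at 3 months", which is not defined further.

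Under Study participants, a patient becomes a drop-out if "Unable to do 2 or more follow up session", or on withdrawal. Missing one follow-up therefore does not make a patient a drop-out.

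The visible text asks for a check of data completeness. It names no imputation, no model for incomplete data, no analysis set, and no rule for a retained patient with one visit missing. The research flow figure is not shown and some pages were removed, so this describes the visible text only.

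**The concern.** Repeated-measures ANOVA in its classical form and the Friedman test both work on complete rows. A patient with months 1 and 3 but not month 2 has no complete row and is left out of the test. The drop-out rule nevertheless treats that patient as still in the study. The plan does not say what happens next, so the named tests decide it by default.

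MMT, FMA-UE and sEMG are all taken at the same visits (Research Work Procedure, step 9). One missed visit would therefore remove the patient from the follow-up p-value in every row of Table 2. The two visits that the patient did attend would add nothing to that p-value, although each includes a substantial recording session: "Muscle signal data were collected for 30 minutes".

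Three things are at stake:

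- the precision of the estimated change over follow-up;
- a stronger assumption than necessary, because a complete-row test relies on attendance being unrelated to recovery, while a likelihood model on all visits needs only data missing at random;
- clarity, because monthly means and the p-value beside them could rest on different patients without the reader being told.

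**Working it through.** **Plan's own figure.** Sample Size Determination uses n = ((1.96 + 1.64) × 1 / 1)² = 12.96, rounded up to 13: "The minimum sample size for the pre-post test group is 13 people". The 10% allowance gives 13 + 1.3 = 14.3, rounded up to 15. Both reproduce. The final 30 comes from a rule of thumb for study types and carries no allowance for loss.

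**Inputs.** From the documents: 30 patients and three follow-ups. Assumed, because the documents give no figure: the chance p of missing a follow-up (5%, 10%, 20%), how far misses cluster within patients, and the correlation between visits.

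**Patients kept but left out of the test**

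- Independent misses: complete rows = 30(1 − p)³; exactly one missed = 30 × 3p(1 − p)². At p = 0.10 these are 30 × 0.729 = 21.9 and 30 × 0.243 = 7.3.
- Clustered misses (beta-binomial, within-patient correlation 0.5): complete rows = 30(1 − p)(2 − p)(3 − p)/6; exactly one missed = 30p(1 − p)(2 − p)/2. At p = 0.10 these are 30 × 0.8265 = 24.8 and 30 × 0.0855 = 2.6.

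| Missed per visit | Complete rows, clustered to independent | Kept but left out, clustered to independent |
|---|---|---|
| 5% | 27.3 to 25.7 | 1.4 to 4.1 |
| 10% | 24.8 to 21.9 | 2.6 to 7.3 |
| 20% | 20.2 to 15.4 | 4.3 to 11.5 |

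Monotone loss (patients who leave do not return, constant hazard) with 10% or 20% lost by month 3: 27 or 24 complete rows, and 1.0 or 1.9 patients missing month 3 only.

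**Precision.** The illustration is the month-3 minus month-1 change, contrast c = (−1, 0, 1). A patient observed at a set of visits O adds X′R⁻¹X to the information on the three visit means, where X selects the visits in O and R is their correlation matrix. Summing over missingness patterns gives the information I, and the variance of the change is c′I⁻¹c. It is computed once from complete rows only and once from all patterns. R is treated as known, with visit correlations 0.6, 0.8 and 0.9, compound symmetric or AR(1).

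| Missed per visit | SE ratio (complete rows / all visits), clustered 0.5 | Independent |
|---|---|---|
| 5% | 1.013-1.020 | 1.040-1.052 |
| 10% | 1.027-1.040 | 1.082-1.109 |
| 20% | 1.055-1.083 | 1.178-1.241 |

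Monotone loss: 1.005-1.014 at 10% and 1.011-1.030 at 20%.

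A simpler case for orientation: 6 of 30 patients each miss one visit, spread evenly over the three. There are 24 complete rows. With compound symmetry and correlation 0.5 to 0.9, the complete-row variance is 1.127-1.139 times the all-visit variance, so the standard error is √1.127 to √1.139, or 1.06 to 1.07 times as large.

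**The case against.** The strongest reply is that the plan contains no contradiction. The drop-out rule says who counts as a drop-out; it does not promise that every retained patient enters every test. A patient who misses month 2 can still contribute to the descriptive columns for months 1 and 3, to the 3-day/discharge test, and to a change between any two visits attended. This stands. A reader might infer that collected data are thrown away. The documents support only that such a patient would be left out of one kind of p-value, and only if a visit is missed.

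The larger figures also need heavy missingness. Independent misses at 10% and 20% per visit mean that 1 − 0.9³ = 27% and 1 − 0.8³ = 49% of patients miss at least one follow-up. The only loss figure in the documents is the 10% exclusion allowance, which is not a visit-miss rate. If 10% of patients missed any visit, independently (p = 3.45% per visit), the standard error would be 2.7-3.6% larger. The contrast used here is also illustrative: the plan specifies an omnibus test, and a known covariance flatters the all-visit analysis at about 30 patients. These points stand and limit the priority.

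A reader might also infer that drop-outs are excluded from analysis, so that patients with both 3-day and month-3 values are lost. The visible text does not state that exclusion, so the point does not rest on it.

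Finally, Friedman protects against non-normality. Contraction counts, amplitudes and a score bounded at 0 and 66 may well be non-normal, so replacing it outright with a linear mixed model would give up a safeguard. This stands and is reflected in the fix.

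What remains is that the named tests, as normally run, cannot use a patient whom the drop-out rule keeps, and no visible text deals with this.

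**Conclusion.** The point holds as a conditional loss of precision in the month 1, 2 and 3 p-values. Under assumed miss rates of 5%, 10% and 20% per visit, 1.4-4.1, 2.6-7.3 and 4.3-11.5 of 30 patients would be kept but left out. The standard error of the illustrative change would be 1-5%, 3-11% and 6-24% larger than with all visits. With monotone loss the increase is at most about 3%; with full attendance it is zero.

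Two stronger readings are not supported. One is that the study becomes too small: complete rows fall below 30 as soon as anyone misses a visit, but they stay above the calculated 13 in every scenario examined. The other is that the results will be biased: nothing in the documents shows that attendance depends on recovery. The comparison also describes change over time. It does not test whether "sEMG parameters can predicts upper extremity motor function recovery in stroke patients", so the prediction question is untouched. Minor priority.

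**What to change.** - For FMA-UE and the sEMG measures, analyse change over follow-up with a linear mixed model, with visit as a categorical factor and all available visits included.
- Check the residuals. Where they are clearly non-normal, transform the measure or keep Friedman as the main test for it.
- Keep the planned repeated ANOVA or Friedman test on complete rows as a sensitivity analysis.
- Keep a rank-based test for MMT, since an ordinal model may be unstable at about 30 patients.
- Report the number analysed at each visit and behind each p-value in Table 2.

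The cost is a change of wording and slightly more analysis work, with no new visits or measurements. The model can be run in the SPSS version that the plan names. It assumes data missing at random, so bias from recovery-related attendance, if there is any, would be reduced but not removed.

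### Every test is judged at p<0.05 and none is named as the one that decides the hypothesis, so the plan has no error control for its claim about sEMG; the tests it lists measure change, not prediction

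*Combined protocol and SAP*

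**What the plan says.** - **Hypothesis:** there is one H0/H1 pair. The alternative reads "H1: sEMG parameters can predicts upper extremity motor function recovery in stroke patients". It names no parameter, muscle or time point.
- **Sample Size Determination:** "Type I error is determined as 5%, hence two-ways hypothesis" with Z = 1.96, and "Type 2 error determined as 5%, hence" Z = 1.64, for one paired comparison of means. The outcome being compared is not named. The formula gives 13, a 10% allowance brings it to 15, and a rule of thumb then sets the minimum at 30.
- **Data Analysis:** "The significance of statistical test results is determined based on a p value of" below 0.05. The listed tests are the paired t-test or Wilcoxon test, repeated-measures ANOVA or Friedman test, and McNemar or marginal homogeneity tests.
- **Dummy Table, Table 2:** five rows (MMT, FMA-UE, contraction, length of contraction, amplitude). Each has one p-value for day 3 against discharge and one for months 1 to 3. The note repeats "The significance value is based on a p value of <0.05" and puts an asterisk on every result that meets it.
- **Outcome Measures:** MMT, FMA-UE and the three sEMG parameters are listed side by side, with none ranked first.
- **Study Variable, Operational Definition and the examination form (Lampiran 1):** sEMG is defined and recorded separately for five muscles.

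Operational Definition ties recovery to FMA-UE but does not call it primary.

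**The concern.** A 5% type I error means something for a hypothesis only if it is clear which result rejects that hypothesis. Here the hypothesis speaks of sEMG parameters in the plural, several p-values are produced for them, each is starred below 0.05, and nothing says how many or which must be significant. An investigator who followed the plan exactly could find one or two starred sEMG rows and report them as support for H1. Study Benefits expects the results to help with prognosis, discharge planning and public policy, so a chance finding presented as confirmation would matter.

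The listed tests also compare each variable with itself over time. A starred row shows that the variable changed. It does not show that an early sEMG value predicts later function.

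**Working it through.** **1. The plan's own figure.** With Z values 1.96 and 1.64, S = 1 and difference = 1:
n = ((1.96 + 1.64) × 1 / 1)² = 3.60² = 12.96, rounded up to 13. Adding 10%: 13 + 1.3 = 14.3, rounded up to 15. Both reproduce. The calculation covers one test at 5%.

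**2. Number of tests.**
- Table 2 as printed: 5 rows × 2 p-values = 10. The sEMG rows alone: 3 × 2 = 6.
- Table 2 filled for each muscle: 5 muscles × 3 parameters = 15 sEMG variables, plus MMT and FMA-UE = 17. Then 17 × 2 = 34 p-values, of which 15 × 2 = 30 are for sEMG.

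The p-value column of Table 3 is left out because it concerns patient characteristics.

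**3. Chance of at least one p<0.05 when nothing changes over time.** For k independent tests this is 1 − 0.95^k. For correlated tests it was simulated with 200,000 draws of normal test statistics sharing a common correlation. The documents give no correlations, so those columns are assumptions.

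| Tests | Independent | 0.3 | 0.5 | 0.7 |
|---|---|---|---|---|
| 6 (printed, sEMG) | 1 − 0.95^6 = 26% | 24% | 21% | 16–17% |
| 10 (printed, all) | 1 − 0.95^10 = 40% | 35% | 29% | 21% |
| 30 (per muscle, sEMG) | 1 − 0.95^30 = 79% | 66% | 51% | 34% |
| 34 (per muscle, all) | 1 − 0.95^34 = 83% | 70% | 54% | 35% |

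At correlation 0.9 the 6 printed sEMG tests still give about 11%. The rate returns to 5% only at correlation 1. The simulation treats every test as a two-sided normal test. Half of the p-values come from three-time-point comparisons, so the correlated figures are approximate.

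**4. Which null these rates refer to.** The null in step 3 is no change in a variable between visits. H0 in the protocol is that sEMG does not predict recovery. None of the tests in Data Analysis or the Table 2 note relates an early sEMG value to a later motor score. The error rate for H0 is therefore undefined, and the table in step 3 does not estimate it.

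**5. What 30 patients offer for an association test.** Using Fisher's z for an unadjusted correlation, power ≈ Φ(atanh(r) × √(n − 3) − z), with √27 = 5.196:
- At 0.05 (z = 1.960), r = 0.4 / 0.5 / 0.6 (assumed): atanh(r) × 5.196 = 2.20 / 2.85 / 3.60, so power is 60% / 81% / 95%.
- At 0.05/15 = 0.0033 (z = 2.935): 23% / 47% / 75%.

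If 10% of the 30 are lost, n = 27 and √24 = 4.899, and power at 0.05 is 55% / 77% / 92%.

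**The case against.** Four points can be made in the plan's defence.

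- **The printed table is short.** Table 2 has 10 p-values, and 34 requires a per-muscle layout that the table does not state. This stands: 34 is a conditional upper bound. The narrowest count, 6, still gives 16–26% over the range of correlation shown, and a single row per parameter leaves unsaid how five muscles are combined.
- **The outcomes are correlated.** They probably are, which is why a range is shown. Correlation reduces the excess over 5% but does not remove it.
- **The 5% is only an input to a sample-size formula.** This also stands. The document does not claim 5% across all tests, and each test can keep its nominal rate. A reader might infer that the stated type I error is false. The supportable statement is that error across the tests is not addressed, and that nothing links the 5% to a decision on H0.
- **The tests concern change, and change is expected.** The Premise section expects the greatest improvement in the first weeks, so a starred row may well be a true change. A reader might infer that H0 will be wrongly rejected 26% to 83% of the time. The documents do not support that: they never say that a Table 2 p-value rejects H0, and the rates rest on a different null.

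The plan cannot be excused as exploratory. It does not describe itself so, and it sets out H0, H1, a 5% two-sided error, 95% power and a significance rule.

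**Conclusion.** The point holds in a limited form. The plan has one hypothesis and one stated error rate, but no primary test, no multiplicity rule and no result designated to decide H0. For the change-over-time tests as printed, the chance of at least one false positive is 40% for all 10 and 26% for the 6 sEMG tests if independent, falling to about 21% and 16–17% at correlation 0.7. The per-muscle figure of 83% (about 35% at correlation 0.7) is an upper bound that depends on how Table 2 is filled. All of these assume no change over time, and the correlations are assumed.

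None of them is the error rate for the prediction hypothesis, which has no test in the plan. That gap matters more than the count: correcting the Table 2 p-values for multiplicity would still leave H0 untested.

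**What to change.** In Data Analysis:

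1. Name one primary test of H0. For example, regress 3-month FMA-UE on one pre-chosen day-3 sEMG parameter, averaged over the five muscles, with day-3 FMA-UE as a covariate, two-sided 0.05. State that H1 is accepted only on that test. The parameter must be fixed before the data are examined.
2. Analyse the other day-3 sEMG parameters and the individual muscles against 3-month FMA-UE as one secondary family with Holm adjustment, and list its members. With 15 muscle-by-parameter tests, the first step is 0.05/15 = 0.0033.
3. Label the Table 2 change-over-time p-values descriptive, and say whether the table is filled per muscle or how muscles are combined.
4. In Sample Size Determination, state that the 95% power refers to a paired mean difference and not to the primary association test, and give the power for the latter.

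**Cost.** No new data are needed, since day-3 and 3-month assessments are already scheduled. This is more than a wording change: it adds an association analysis that the current calculation does not cover. With 30 completers, an unadjusted correlation test has about 60% / 81% / 95% power at 0.05 for r = 0.4 / 0.5 / 0.6, and 23% / 47% / 75% at the first Holm step of 0.05/15. With day-3 FMA-UE in the model, the r that matters is the partial correlation, for which the documents give no value. Secondary sEMG claims will face a distinctly stricter threshold.
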